6.1.3 Secondary Endpoints

The secondary endpoints of this study include:

- Achilles infusion set device function as evidenced by the absence of device failure with or without uncontrolled hyperglycemia. Device failure is defined as:
 - Cannula dislodgement from subcutaneous space (with or without liquid leakage at the cannula infusion site), or
 - other Achilles device malfunction (e.g., inability to pierce skin, bending, kinking or other malformation that might impact insulin infusion, securement failure).

SEE ABOVE NOTE
- Standard glucose control measures obtained from Continuous Glucose Monitoring, including observed hyper- and hypoglycemic episodes.
- Subject tolerability levels for the initial manual Achilles infusion set insertion, daily wear and final removal will be assessed using a visual analog pain scale (VAS).
- The incidence, seriousness and potential relationship infusion site to the investigation device of all adverse events will be documented and reported.

6.1.4 Variables to Assess

The variables assessed in this study include:

- Frequency of pump prime events (i.e infusion set change out) as evaluated from the 14d pump data downloaded during the screening visit as well as during the evaluation periods

- Interstitial glucose values as measured by the CGM, downloaded at each visit to the study center
- Capillary blood glucose values measured by fingerstick measurements, downloaded from the glucose meter/recorded in Patient Diary
- Ketone values measured by fingerstick measurements, downloaded from the ketone meter/recorded in Patient Diary
- Daily pain assessments from the VAS recorded in Patient Diary
- Number of Achilles infusion set failures per definition in sections 6.1.2 and 6.1.3
- Number of hyperglycemic events (CGM, Patient Diary)
- Number of hypoglycemic events (CGM, Patient Diary)

6.1.5 Test Equipment to Use

- Dexcom G5CGM (calibration differs per model) for continuous monitoring of blood glucose level and collection of data. For the G5 model, calibration is needed at least once every 12 hours with a manual BG meter measurement.
- Ascencia Contour Next glucose monitor plus SMBG test strips for manual blood glucose monitoring for confirmation of CGM data and in the case of adverse events. Calibration with a control solution is recommended when using the meter for the first time, new box of test strips is opened, or to verify meter and test strips are working properly.
- Abbott Precision Xtra ketone monitor plus test strips for confirming hyper/hyperglycemic events. Calibration with a control solution is recommended when using the meter for the first time, new box of test strips is opened, or to verify meter and test strips are working properly.

6.2 Participants

6.2.1 Inclusion Criteria

Patients must meet all of the following criteria to be included in the Study:

- 1) Participants are 18 – 70 years of age inclusive
- 2) Subject is in generally good health, as determined by the investigator
- 3) Subject is willing and able to individually complete written informed consent and agrees to comply with all study related testing and examinations
- 4) Subject must be geographically stable (e.g., expects to be available and capable of returning for all study specified test and examinations) during the study period
- 5) Subject has been diagnosed with T1DM for at least 12 months
- 6) C-peptide <0.6 nmol/L at screening
- 7) Subject can provide a minimum of 14 days of insulin pump data to demonstrate pump use compliance

- 8) Subject is willing to perform serum ketone measurements whenever the blood glucose is determined to be greater than 250 mg/dL using a ketone meter and strips provided by the sponsor
- 9) Subject has BMI in the range 20 – 35 kg/m² inclusive
- 10) Subject has experience infusing a rapid-acting insulin analog for at least 6 months
- 11) Subject has been using an insulin pump with commercially available infusion sets for at least 6 months (this includes Automated Insulin Delivery systems)
- 12) Subject has been using a continuous glucose monitor (CGM) for at least 3 months
- 13) Subject has ability to understand and comply with protocol procedures and to provide informed consent
- 14) AST and ALT \leq 120 U/L
- 15) Creatinine <1.8 mg/dL

6.2.2 Exclusion Criteria

Patients who meet any of the following criteria will be excluded from study participation:

- 1) Participants whose average total daily insulin dose exceeds 85 units/day (i.e. typically change insulin reservoirs more often than every 3.5 days on average)
- 2) Participants who routinely change their commercial insulin infusion sets twice weekly or less often (wear time > 3.5 days)
- 3) Female subject is pregnant or nursing²
- 4) Participant has abnormal skin at intended device infusion sites (existing infection, inflammation, burns, or other extensive scarring)
- 5) Subject has HbA1C > 8.5% at screening
- 6) Participant has documented history in last 6 months of severe hypoglycemia associated with cognitive dysfunction sufficiently severe to require third party intervention or a history of impaired awareness of hypoglycemia.
- 7) Participant has a history of diabetic ketoacidosis in the last 6 months
- 8) Participant has known cardiovascular disease considered to be clinically relevant by the investigator
- 9) Participant has known arrhythmias considered to be clinically relevant by the investigator

² Documented negative pregnancy test results for female participants required unless participant is menopausal without any spontaneous menstrual cycles for >12 months or key organs have been removed.

- 10) Participant has known history of:
 - a) Cushing's Disease,
 - b) pancreatic islet cell tumor, or
 - c) insulinoma
- 11) Participant has:
 - a) Lipodystrophy,
 - b) extensive lipohypertrophy, as assessed by the investigator
- 12) Subject is undergoing current treatment with:
 - a) Systemic oral or intravenous corticosteroids,
 - b) monoamine oxidase (MAO) inhibitors,
 - c) non-selective beta-blockers,
 - d) growth hormone,
 - e) thyroid hormones, unless use has been stable during the past 3 months
- 13) Subject has significant history of any of the following, that in the opinion of the investigator would compromise the subject's safety or successful study participation:
 - a) Alcoholism,
 - b) drug abuse
- 14) Significant acute or chronic illness, that in the investigator's opinion, might interfere with subject safety or integrity of study results
- 15) Planned operation, MRI or CT which require removal of infusion set or CGM sensor during wear periods
- 16) Current participation in another clinical drug or device study
- 17) AST and ALT >120 U/L
- 18) Creatinine \geq 1.8 mg/dL

6.2.3 Withdrawal

Any study participant who has been enrolled (i.e. had a first attempt to insert the Achilles infusion set) and decides either to discontinue participation or withdraw from the study prior to the end of week 1 evaluation period will be considered a study dropout. If a participant withdraws from the study due to an adverse event/complication, the subject should be followed and all data collected through resolution of the adverse event.

Participant will be exited at the time of discontinuation/withdrawal or upon resolution of any medical complications/adverse events. All data up to the point of study exit will be documented

and entered into the study database. Participants who are dropouts or exit the study before completion of both 7-day evaluation periods will be counted in the total cohort enrollment and Intent-to-Treat and Per Protocol analysis populations.

6.2.4 Point of Enrollment

Potential patients will be screened for study participation based on the eligibility criteria. After completing written informed consent, eligible participants shall be assigned a unique study identifier.

Eligible participants will be considered “enrolled” at the time of the first attempt to insert the investigational Achilles infusion set. Enrolled participants will have an Achilles infusion set inserted and secured by study staff, followed by three extended home wear periods of up to 1 week (0-7 days) each.

6.2.5 Duration

Including screening up to 21 days prior to first study visit (Day 0a), the study duration for each patient will be about 6 weeks.

6.2.6 Number of Participants

20 participants will be enrolled in this feasibility home use trial.

6.3.7 Enrollment Period

Participants will be screened and tested to verify study eligibility criteria, including a physical exam, complete medical history and laboratory testing. Female participants of child-bearing age who do not have a documented history of menopause (defined as at least 12 months without a spontaneous menstrual period and/or removal of key organs) must undergo a urine pregnancy test within 7 days of the planned intervention date. All participants must also undergo a complete blood and metabolic panels within the required screening period.

Patients with positive c peptide value (defined as c-peptide >0.6 nmol/L) may be rescreened for study eligibility one time within 2 week of initial test date.

6.3 Study Procedures

6.3.1 Clinical Investigation

See Section 2.9 and Figure 1.

6.3.2 Sponsor Representative Involvement

The Sponsor and Manufacturer Capillary Biomedical will provide all investigational Achilles infusion sets. The Local Sponsor is responsible for supplying and all relevant study material such as glucose meters, ketone meters, test strips, and CGM and reimbursing study participants and insurance.

6.3.3 Potential Factors That May Compromise Outcome or Interpretation

Potential factors that may affect the outcome of the study or interpretation of the data include but are not limited to the duration of CSII therapy and/or CGM sensors and the resulting changes in skin/tissue structure. Frequent rotations of infusion/sensor sites can compromise the skin structure due to connective tissue disruption and scarring. (E.g., the skin and subcutaneous tissue of a patient who has been on CSII therapy for only 2 years may differ substantially from that of a patient who has been using an insulin pump for a decade.) In order to minimize the influence of scar tissue on study outcomes, areas of scar tissue and/or lipohypertrophy will be avoided as sites for insulin infusion or CGM.

6.4 Monitoring Plan

6.5.1 Safety Oversight

Unanticipated Adverse Device Effects and Serious Adverse Events will be reported to the Sponsor within 24 hours of knowledge of the event. Sponsor shall endeavor to review such events within 24 hours of notification. Preliminary event seriousness and device relationship will be assessed by the principal investigator or a qualified designee.

A qualified clinician shall act as the study Medical Monitor. Adverse events shall be reviewed at least monthly by Sponsor and/or Medical Monitor. Serious or unanticipated adverse events shall be reviewed upon receipt of full documentation of the event, including any sequelae and treatment required for resolution. The Medical Monitor will document event review and adjudication.

6.5.2 Clinical Monitoring

Clinical monitoring is an ongoing process conducted to ensure that the rights and well-being of study participants are protected, that the reported trial data are accurate, complete, and verifiable, and that the conduct of the trial is in compliance with the currently approved protocol/amendment(s), with applicable Good Clinical Practices and regulatory requirement(s).

Capillary Biomedical or a qualified designee shall be responsible for site monitoring. Monitors will be qualified by training and experience. Monitor(s) will be familiar with the investigational product, protocol, consent form and any other written information given to the participant,

study SOPs, GCP and other relevant regulatory requirements. Training and qualification of Monitor(s) shall be documented in writing.

Monitoring will be performed as a combination of periodic on-site and remote monitoring based on enrollment rate, occurrence of adverse events, and site compliance issues to assess consent procedures, subject eligibility, adverse events, device accountability, and primary endpoint data. Monitoring reports shall be due to Sponsor management per applicable SOP timeframes.

6.5.3 Quality Assurance and Quality Control

All measures have been taken to minimize subject risks before, during and at the end of the study. Standard operating procedures will be employed during study planning, conduct and analysis stages.

A standardized protocol, case report forms, data sheets, diaries and examination schedules will be used to collect data consistent with the study objectives and evaluation endpoints. Written informed consent will be required from each subject prior to initiation of any study specific testing or examinations.

Study investigators shall perform the study per the currently approved protocol requirements and procedures. Protocol deviations shall be documented in writing and reported to the governing IRB. The clinical site staff shall be responsible for study conduct per protocol, the collection, labeling and storage of biological specimens per site requirements and all applicable patient privacy rules, the documentation and completion of study case report forms, logs, etc.

Periodic source document monitoring shall be conducted throughout study conduct and follow-up periods. Following written Standard Operating Procedures (SOPs), the monitors will verify that the clinical trial has been conducted in compliance with the protocol, biological specimens are collected, documented (recorded), and reported in compliance with all local and federal requirements, applicable Good Clinical Practices and all other applicable regulatory requirements.

The investigational site will be required to provide access to all study source data/documents to sponsor and sponsor representatives for monitoring purposes as well as to regulatory authorities during inspections.

7 Statistical Analysis

7.1 General Approach

As a routine evaluation of the data during analysis, consistency of the study variables to properties of statistical tests will be checked. Descriptive statistics shall be used for independent variables.

For tabulated continuous variables, descriptive analyses will present the mean, standard deviation, median, minimum and maximum. For tabulated categorical variables, the number with the characteristic, the total number evaluated and the percent will be provided.

Unless otherwise specified, statistical analyses will be performed using vendor specified software products.

7.2 Populations for Analysis

Intent-to-Treat (ITT) Analysis Population: All participants who meet all eligibility criteria and have undergone a first attempt to insert an investigational Achilles infusion set shall be included in the ITT analysis population.

Safety Analysis Population: All participants who had an investigational cannula inserted.

Per-Protocol (PP) Analysis Population: All patients who completed any part of the 7-day Achilles infusion set evaluation period.

The primary effectiveness analysis will be based on the ITT subject population. Sensitivity analyses of the primary effectiveness endpoint will be generated based on the PP population. The ITT population may contain some patients who did not complete the evaluation interval. This will require the use of imputation methods for missing values. Last observation carry forward will be used in such case.

The primary safety analysis will be based on the safety population. All secondary and exploratory effectiveness analyses will use both the ITT and PP populations.

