7.3 Analysis of the Primary Efficacy Endpoint

The primary study endpoint is the proportion of Achilles infusion sets that function each day of use, up to 7 days. This endpoint will serve as both the preliminary effectiveness and safety endpoint during the feasibility evaluation.

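### The Per-Protocol set in 7.2 excludes nobody for a protocol deviation, 6.2.3 and 7.2 disagree on failed Day 0a insertions, and the Safety set may leave those participants out

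*Combined protocol and SAP*

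**What the plan says.** Section 7.2 defines three sets.

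- ITT: "All participants who meet all eligibility criteria and have undergone a first attempt to insert an investigational Achilles infusion set".
- Safety: "Safety Analysis Population: All participants who had an investigational cannula inserted".
- PP: "All patients who completed any part of the 7-day Achilles infusion set evaluation period".

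ITT carries the primary effectiveness analysis. For PP, 7.2 says "Sensitivity analyses of the primary effectiveness endpoint will be generated based on the PP population". Secondary and exploratory effectiveness analyses use both ITT and PP. For safety, "The primary safety analysis will be based on the safety population". The missing-data sentence, "Last observation carry forward will be used in such case", follows directly on a remark about incomplete ITT participants. No rule is given for PP.

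Four other sections bear on membership.

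- 6.2.3 counts "Participants who are dropouts or exit the study before completion of both 7-day evaluation periods" in total enrollment, in ITT and in PP.
- 6.2.4 places enrollment of eligible participants at the first insertion attempt.
- 2.9 exits a participant from the study after three failed attempts on Day 0a.
- 7.3 says of the primary endpoint, the proportion of sets functioning on each day of use: "This endpoint will serve as both the preliminary effectiveness and safety endpoint during the feasibility evaluation".

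**The concern.** A PP analysis is normally run to see whether the result survives once participants who departed from the protocol are removed. Here the definition removes none of them. Section 10 defines deviations, but 7.2 does not use that definition. A PP result close to the ITT result would look like reassurance about deviations and would not be.

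The other two problems concern one kind of participant: someone enrolled at the first attempt in whom no set could be placed on Day 0a. Insertion failure is a listed device risk (5.5), and the device is first-in-human (5.3). Two sections give different answers on whether that participant is in PP, and the Safety definition may leave the participant out of the primary safety analysis. At stake is whether insertion failures appear in the denominators of the sensitivity and safety tables.

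**Working it through.** There is no planned figure to reproduce. The sample size of 20 (6.2.6) rests on similar studies, with no hypothesis (5.3). The check is to apply each definition to particular participants.

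| Participant | ITT (7.2) | PP by 7.2 | PP by 6.2.3 | Safety (7.2) |
|---|---|---|---|---|
| Eligible, exited after three failed Day 0a attempts | in | out (no part completed) | in (early exit) | out, if the word inserted is read strictly |
| Eligible, major deviation, wears all sets to the end | in | in | not addressed | in |
| Ineligible, enrolled in error, wears all sets to the end | out | in | not addressed | in |
| Eligible, wears only the saline set, then withdraws | in | open | in | in |

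Row 1 shows the conflict between 6.2.3 and 7.2, and the gap in Safety. Row 2 shows that a deviator stays in PP. Row 3 shows that PP need not lie within ITT. Row 4 is open because 7.2 speaks of one 7-day period without naming it: 2.9 calls the saline Week 1 an evaluation period, while 6.2.3 speaks of two periods and 6.2.4 of three.

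Only Day 0a matters for Safety. Week 2 follows successful completion of Week 1 (1.4.1), so anyone reaching Day 0b has already had a cannula inserted.

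**Size in Week 1.** The documents give no insertion-failure rate, so the following counts are assumptions. Take N = 20 enrolled, all eligible, with f exits after failed Day 0a attempts and w other Week 1 device failures.

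- ITT, and PP by 6.2.3: (f + w)/20.
- Safety read strictly, and PP by 7.2: w/(20 − f).

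| f | w | ITT and PP by 6.2.3 | Safety and PP by 7.2 |
|---|---|---|---|
| 1 | 0 | 1/20 = 5% | 0/19 = 0% |
| 2 | 0 | 2/20 = 10% | 0/18 = 0% |
| 3 | 0 | 3/20 = 15% | 0/17 = 0% |
| 1 | 2 | 3/20 = 15.0% | 2/19 = 10.5% |
| 2 | 2 | 4/20 = 20.0% | 2/18 = 11.1% |
| 3 | 2 | 5/20 = 25.0% | 2/17 = 11.8% |

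With f = 0 the two columns agree. If each participant's chance of three failed attempts is q, the chance of at least one such exit among 20 is 1 − (1 − q)^20. That is 18%, 33% and 64% for q = 1%, 2% and 5%.

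**Size in Weeks 2 and 3.** The endpoint in 7.3 counts infusion sets. A Day 0a exit never receives a Week 2 or Week 3 set and so adds nothing to the numerator or denominator there, whichever set the participant belongs to. This holds unless carrying forward is read as imputing sets that were never placed, which 7.2 does not say.

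**The case against.** **Eligibility is covered at entry.** Section 6.2.4 enrolls eligible participants only. This stands in part. A reader might infer that PP is larger than ITT by design, but that happens only if someone is enrolled in breach of 6.2.4. With one such person who wears every set, and no failed insertion, PP is 20 and ITT is 19; with none, both are 20. The missing deviation condition does not depend on this.

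**The conflict is inferred.** Section 6.2.3 is headed as a withdrawal rule and does not mention failed insertions. They come under it only through the exit rule in 2.9. That is correct, but the wording of 6.2.3 covers anyone who exits early, so both sections apply.

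**A partial placement might count as inserted.** Section 5.5 describes insertion failure as holes left above the skin layer, which could mean a partly placed cannula. The exclusion from Safety is therefore possible, not certain.

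**Device failure may never be tabulated on Safety.** Section 7.5 lists only pain scores and adverse events. The route to a Week 1 proportion on the Safety set is the dual-use sentence in 7.3, so the Safety column above applies only where such a table is made.

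**Success is not affected.** A reader might set 6/20 = 30.0% against 6/19 = 31.6% and conclude that one failed insertion could carry the study past the 30% benchmark in 5.4. The documents do not support that. The Week 2/3 proportion is per set, these exits contribute no insulin set, and 5.4 does not say that PP decides success.

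**Adverse events are not lost.** Section 6.1.3 has all of them documented and reported, and the by-patient listings in 7.7 would let a reader rebuild the sets. What remains is set membership and the denominators used.

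**Conclusion.** The point holds, at minor to moderate weight. As written, the PP sensitivity analysis cannot show robustness to protocol deviations. Whether it says anything about dropouts is undetermined, because no missing-data rule is stated for PP. Sections 6.2.3 and 7.2, read with 2.9, disagree on PP membership after failed Day 0a insertions, and Safety may omit those participants.

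The numerical effect is limited to Week 1 device-failure proportions where they are tabulated on PP or Safety: 5 to 15% against 0% for one to three exits among 20 with no other Week 1 failure. That rests on assumed counts, on all participants being eligible and on a strict reading of inserted. It is zero if no Day 0a insertion fails. These exits alter neither the primary ITT analysis nor the Week 2/3 per-set proportion.

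**What to change.** 1. In 7.2, define Safety as every participant with at least one insertion attempt.
2. Delete the PP clause from 6.2.3. In 7.2, define PP as ITT participants without a major protocol deviation, list the major deviations in advance, and name the wear period or periods covered. Do not exclude anyone for device failure or early exit as such.
3. State that failed insertions count as device failures in the device-function endpoint and not in the Week 2/3 hyperglycemia/occlusion endpoint. Reconcile the synopsis overview (1.4.1), where inability to pierce the skin in Week 1 is a secondary outcome, with 6.1.2 Primary Endpoint, where it is a Week 1 primary endpoint event.
4. State that PP uses the same missing-data method as ITT, so that a difference between the two reflects deviations alone. Whether last observation carried forward suits this endpoint is a separate question.

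The cost is wording in these sections and a short list of deviations. PP may become slightly smaller and the safety denominator slightly larger. No visit, procedure or sample size changes.

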After insertion of the Achilles infusion set at the study site, participants will be required to manage routine basal/bolus insulin therapy using study specific supplies only with their current insulin pump during two extended wear home use periods of up to 7 days each (*Week 2* and *Week 3*, respectively). Participants will monitor BG levels with Dexcom G5 CGM device to avoid glycemic excursions. Participants will conduct daily visual inspection and record Achilles insertion set location pain levels and skin reactions. If subject experiences an Achilles infusion set device issue, participants shall insert a commercial CSII set to maintain routine insulin therapy. Participants will be provided with training and written instructions if an Achilles device issue occurs at any time during home wear periods. They are instructed to contact study staff as early as possible after infusion set failure. *Week 2* evaluation period is complete when either, 1) an Achilles infusion set failure occurs and subject needs to insert a commercial CSII set to maintain routine therapy until they return to the study center, or 2) subject has worn Achilles for the total 7-day wear period.

Upon completion of *Week 2* wear period (either after full 7 days or earlier), participants are asked to return to study center. Data will be downloaded from the subject's insulin pump, ketone monitors and CGM. Patient Diaries will be collected after each wear period. All study supplies will be replenished as needed.

Week 3 evaluation begins when study center inserts another Achilles infusion set (Day 0c). Participants will maintain insulin pump therapy per standard of care. *Week 3* home use evaluation is considered complete when, 1) an Achilles device issue requires subject to insert a commercial CSII set; or 2) subject has worn Achilles for a second total 7 -day wear period.

Participants who do not participate in *Week 3* will exit the study at time of declination. All data up the point of study exit will be documented and included for analysis. Participants may exit the study at any time without prejudice to their ongoing medical care. The time and reason for early exit will be recorded, and all data up to the point of study exit shall be documented and included for analysis.

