5.4 Intended Performance/Success Criteria

Results of this study will be compared to those of Patel et al. (3), who observed that 30% of infusion sets performed adequately (no premature failure due to mechanical malfunction and no episodes of uncorrectable hyperglycemia prior to the end of 7 days of infusion set wear time), and, among infusion sets that did not exhibit mechanical malfunction, 60% performed adequately by the glucose control metrics for the 7-day wear period. Success criteria will be considered met if the Achilles infusion set exceeds these performance outcomes.

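### Within a wear period, carrying the last observation forward scores a set that exits while working as functioning to Day 7, so for such sets any bias is upward

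*Combined protocol and SAP*

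**What the plan says.** Section 7.2 makes ITT the primary effectiveness population and anticipates incomplete follow-up: "The ITT population may contain some patients who did not complete the evaluation interval". The stated remedy is "Last observation carry forward will be used in such case".

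Section 7.3 gives the quantity this applies to: "The primary study endpoint is the proportion of Achilles infusion sets that function each day of use, up to 7 days".

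Sections 1.4.1 and 2.9 end a Week 2 or Week 3 wear at set failure or at 7 days. Section 2.9 also allows exit during a wear: "Participants may exit the study at any time without prejudice to their ongoing medical care". It adds that "The time and reason for early exit will be recorded".

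Under section 6.2.3, dropouts and early exits "will be counted in the total cohort enrollment and Intent-to-Treat and Per Protocol analysis populations". Section 7.2 likewise admits to the per-protocol (PP) population anyone who completed any part of the wear.

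Section 5.4 sets the yardstick. In a cited study, 30% of sets performed adequately, meaning "no premature failure due to mechanical malfunction and no episodes of uncorrectable hyperglycemia prior to the end of 7 days" of wear. Among sets without mechanical malfunction the figure was 60%. The decision rule is "Success criteria will be considered met if the Achilles infusion set exceeds these performance outcomes". No margin or confidence bound is attached to it.

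**The concern.** A failed set has no missing later status, because failure ends the wear and is itself observed. Within a wear, the days that need imputing belong to a set whose wearer left while it still worked. Its last status is functioning, and carrying that to Day 7 assumes no risk of failure after exit. The protocol's own Table 1 (section 4.7) has infusion set failure rising from above 25% at Day 3 to above 65% at Day 7, so that assumption is hard to defend.

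The resulting proportion is compared with 30% by simple exceedance, so a small upward shift can decide the comparison for a device near the benchmark. The plan gives no censoring rule and no worst-case analysis. The PP analysis keeps early exits, and the plan does not say whether PP is imputed, so it is not a dependable check. The listings in section 7.7 may let a reader find the affected sets, but the reported proportion would still include them as successes.

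**Working it through.** **Direction.** Take N sets in a wear period, F observed failures and C exits while working, of which x would have failed by Day 7.

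- Carry-forward gives (N − F)/N.
- Full follow-up would give (N − F − x)/N.
- The difference is x/N, which is never negative. It is zero if C = 0 or if x = 0.

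Enumerating every (F, C, x) gave no exception in 1,771 combinations for N = 20 and 12,341 for N = 40. Carry-forward was also never below Kaplan-Meier in 20,000 random data sets of 40 sets.

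**A count example.** With 40 sets, 26 failures and 4 working exits:

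- carry-forward: 14/40 = 35.0%
- completed wears only: 10/36 = 27.8%
- exits counted as failures: 10/40 = 25.0%

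Of these three, only carry-forward exceeds 30%.

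**Inputs for size.** From the documents: the 30% benchmark (5.4), 7 days of wear, and 20 participants (6.2.6). Two insulin wears each give at most 40 sets. Assumed: true Day-7 function of exactly 30%, constant daily failure risk, independent sets, and exits at Day 3 unrelated to function. The exit share f is also assumed. It is a share of the sets still working at Day 3, not of all wears.

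**Formulas.**

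- Daily survival s = 0.30^(1/7) = 0.842, so s³ = 0.597 and s⁴ = 0.503.
- Expected working exits among 40 sets at f = 5%: 40 × 0.597 × 0.05 = 1.2.
- Mean under carry-forward: (1 − f) × 0.30 + f × 0.597. At f = 5% this is 0.285 + 0.030 = 31.5%. At f = 10% it is 0.270 + 0.060 = 33.0%.
- Each working exit at Day 3 adds (1 − s⁴)/N on average: 0.497/40 = 1.24 points, or 0.497/20 = 2.49 points.

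**Chance of exceeding 30%**, by exact enumeration. The number working at Day 3 is Bin(N, s³). Exits are binomial among these with probability f. Day-7 survivors are binomial among the rest with probability s⁴. A result of exactly 30% does not pass.

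| f | Mean, carry-forward | 40 sets: carry-forward vs Kaplan-Meier | 20 sets: carry-forward vs Kaplan-Meier |
|---|---|---|---|
| 0% | 30.0% | 42.3% (both) | 39.2% (both) |
| 2.5% | 30.7% | 46.4 vs 45.2% | 42.1 vs 41.5% |
| 5% | 31.5% | 50.4 vs 46.7% | 44.9 vs 43.1% |
| 10% | 33.0% | 58.4 vs 48.0% | 50.7 vs 45.1% |
| 20% | 35.9% | 72.8 vs 48.3% | 61.7 vs 46.6% |

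The Kaplan-Meier mean stays at 30.0%. Its pass chance still moves with f, because censoring makes results of exactly 30% less common. The part due to carry-forward is therefore the gap between the two columns at the same f: 50.4 − 46.7 = 3.7 points at 5% and 58.4 − 48.0 = 10.4 points at 10%, with 40 sets. Counting every exit as a failure gives 34.2% and 26.7%.

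**Better devices, f = 10%, 40 sets.** True 40%: mean 42.8%, pass 93.1 vs 88.8%. True 60%: mean 62.0%, and both methods pass essentially always.

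**Why not every exit should be censored.** Suppose 20% of the sets that would fail on Days 4 to 7 are removed while working at Day 3. That is 0.20 × (0.597 − 0.300) = 0.0594 of all sets, or 2.4 of 40. Carry-forward gives 0.300 + 0.0594 = 35.9%. Censoring them gives 0.597 × 0.300/(0.597 − 0.0594) = 33.3%. Counting them as failures gives the true 30.0%.

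**The case against.** **Carry-forward need not always raise the result.** A reader might infer that the rule biases the proportion upward however it is applied. The documents do not support that. Section 7.2 words the imputation per patient and does not define the evaluation interval across three wear periods. If a Week 2 failure were carried into a Week 3 set never inserted, the proportion could fall. For example, 6/16 = 37.5% in Week 3 becomes 6/20 = 30.0% if four Week 2 failures are carried over. The upward direction holds only within a set. This limit stands.

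**The pass figures are not the chance of study success.** Section 5.4 names two benchmarks, and the figures cover only the 30% one. This also stands.

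**The effect may be small.** No exit rate is given. At f = 5% about 1.2 of 40 sets are affected. Mid-wear exits are made less likely by the eligibility criteria (geographic stability, no planned procedure needing set removal) and by the saline run-in. The non-participation that section 2.9 singles out, declining Week 3, falls between wears. A device at exactly 30% already passes 42.3% of the time with 40 sets and no exits, so the bare exceedance rule matters more than this imputation rule at low exit rates. Section 5.3 also disclaims any definitive hypothesis. All of this limits the size, but the success rule in section 5.4 remains and the direction within a set is unchanged.

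**The PP table might show the problem.** The imputation sentence refers to ITT, and section 7.1 requires the number evaluated beside each percentage, so an unimputed PP table would show its denominator falling by day. That is a fair reading and would help, but the plan does not state it.

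**Conclusion.** The point holds within a wear period. A set that leaves observation while working is scored as functioning through Day 7, and for such sets the Day-7 proportion is overstated or unaffected, never understated. It is unaffected if no working set exits, or if none of those that exit would have failed.

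At a true 30%, the mean rises by 1.5 points if 5% of the sets working at Day 3 exit then, and by 3.0 points if 10% do. With 40 sets, carry-forward adds 3.7 and 10.4 points over Kaplan-Meier to the chance of clearing the 30% benchmark; with 20 sets it adds 1.8 and 5.6. These figures assume the exit share, exit at Day 3, constant risk and independent sets.

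A reader might go further and conclude that the rule would produce a false success. The documents do not show that: they give no exit rate, the 60% benchmark is not modelled, and a device well above 30% is hardly affected. The direction is certain and the importance is moderate. The rule should be changed before data are seen.

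**What to change.** For the primary endpoint, replace carry-forward with a Kaplan-Meier estimate of set function by day, computed set by set, in ITT and PP alike.

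- Censor a set only if it was working at exit and its recorded reason is unrelated to the device or infusion site.
- State that no status is carried into a set that was never inserted.
- Add a worst-case sensitivity analysis counting every early exit as a failure. This also covers removals for discomfort or as a precaution.
- Report whether the comparisons with both section 5.4 benchmarks hold under the main and the worst-case analysis.

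Which events count as failure (dislodgement, signs of infection) and whether Weeks 2 and 3 are pooled are separate questions, and this change does not settle them.

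The cost is one SAP paragraph and one or two extra tables with standard software. Time and reason for exit are already collected, and neither conduct nor sample size changes. The price is a slightly less favourable estimate if working sets do exit.
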